Title: The Impact of Free Fatty Acid Reduction on Vascular Function in the Metabolic Syndrome

NCT00759291

Document Date: February 28, 2008

STUDY PROCEDURES AND PROTOCOL

This study uses a randomized, placebo-controlled crossover design.

After providing informed consent, both groups will undergo an initial screening visit in the Vascular Medicine Research Center. This visit will include a comprehensive health history and physical exam and anthropomorphic data collection (height, weight, body mass index (BMI) and waist-hip ratio). Screening blood tests will be drawn to assess fasting glucose, blood count, lipid profile, glycosylated hemoglobin, and assessment of renal and hepatic function. Baseline serum insulin and nonesterified free fatty acid levels will also be drawn at this visit. An ECG will be performed.

We hypothesize that acipimox, by decreasing plasma FFA concentrations, will augment endothelium-dependent vasodilation in conduit vessels and insulin-mediated vasodilation in forearm resistance arterioles *in vivo*, whole-body insulin sensitivity, and AKT and eNOS phosphorylation in skin biopsy specimens *ex vivo*, when compared with placebo.

Subjects will be studied at 2 separate visits, 4 weeks apart, in a randomized, double-blind crossover design. Subjects will receive either acipimox 250 mg tablets orally every 6 hours, or matching placebo, for 7 days prior to and at 7 am on the morning of the study visit. Each visit will include vascular function testing and a forearm skin biopsy. Forearm blood flow will be measured in the basal state, and with insulin infusion.

Evaluation of vascular function in conduit vessels:

Vascular function of the brachial artery will be measured in all subjects as reported previously by the applicants and recommended by a recent task force (56-58) (also see Preliminary Results Section). To assess endothelium-dependent vasodilation, measurements of brachial artery diameter will be made under basal conditions and during reactive hyperemia following five minutes of an ischemic stimulus. Forearm ischemia will be induced by inflating a blood pressure cuff on the upper part of the arm to suprasystolic pressures for 5 minutes. This results in vasodilation of the downstream resistance vessels. Following release of the cuff, there is a 6 to 10-fold increase in flow through the brachial artery, i.e., reactive hyperemia. Flow is a physiologic stimulus that releases nitric oxide from the endothelium. We have found that the maximal increase in brachial artery diameter occurs at one minute of reactive hyperemia and that this dilation is mediated by nitric oxide (56, 57). Endothelium-independent vasodilation will be assessed by measuring brachial artery diameter under basal conditions and 3 minutes following the administration of sublingual nitroglycerin (0.4 mg) (58). Maximal brachial artery dilation occurs 3 to 4 minutes after the administration of sublingual nitroglycerin.

The diameter of the brachial artery will be measured using high resolution B-mode ultrasonography. An ultrasound scanner (Toshiba model Powervision 8000) equipped with a high resolution linear array transducer (7.5 mHz) is used to image the artery and thus enable measurement of its diameter and cross-sectional area. A longitudinal image (parallel to the artery) is acquired just proximal to the antecubital fossa. The transducer is then positioned at 90 degrees to the vessel to acquire an image through the center of the vessel so that the near and far wall interfaces will be clearly discernible. A simultaneous electrocardiographic signal is recorded. The video output and electrocardiographic

signal of the ultrasound machine is connected to a computer equipped with a Data Translation frame grabber videocard. The R wave on the electrocardiogram is used as a trigger to acquire (digitize) frames. Digitized images at baseline and after intervention (e.g., reactive hyperemia, nitroglycerin) are stored on the hard drive and backed up on removable media. Acquisition and analysis of the stored images is performed using software designed for this purpose by Medical Imaging Applications. The vessel wall lumen interface is determined by derivative based edge detection following identification of the region of the anterior and posterior walls by the investigator. The maximum diameter of the vessel is then determined (59). We have found that this technique yields an interobserver variability of $0.05\pm0.16\%$ and intraobserver variability of $0.01\pm0.15\%$.

Evaluation of vascular function in forearm resistance vessels:

Each subject will be studied in the post-absorptive state, in a quiet, temperature-controlled (23°C) room. Alcohol and caffeine will be withheld for 12 hours prior to the study. In order to evaluate insulin-mediated vasodilator function in forearm resistance vessels, resistance arteriole flow will be determined before and during euglycemic, hyperinsulinemic clamp. Measurement of insulin-mediated vasodilation will be made in each study condition (placebo & drug) before and during hyperinsulinemic clamp. Forearm blood flow will be determined by venous-occlusion strain-gauge plethysmography, as described previously by this laboratory (60, 61). Forearm blood flow (FBF) will be derived from the rate of change in forearm circumference during venous occlusion and will be expressed at ml/100 ml tissue/minute. Each determination of forearm blood flow will comprise at least five separate measurements. FBF measurements will be recorded on a Hokanson AI6 physiologic recorder.

Hyperinsulinemic Clamp

A whole-body hyperinsulinemic- euglycemic clamp will be created via an intravenous infusion of insulin. A primed constant insulin infusion of $80\text{mU}/\text{m}^2/\text{min}$ is started and continued for 120 minutes. This dose has been demonstrated to attain typical postprandial insulin concentrations, facilitating evaluation of both initial-phase and steady-state insulin-mediated vasodilation (65). Contralateral cubital vein glucose will be measured every 5 minutes to ensure a constant glucose concentration of 5.1 mmol (90 mg/dL). Adjusted dextrose 20% solution will be infused intravenously to maintain this concentration. Systemic glucose and insulin concentrations will be determined from the control arm cubital vein. Whole body insulin sensitivity will be quantified by determining M , (metabolized glucose) during the final 5 steady-state measurements. M will be calculated as the glucose infusion rate, adjusted according the method described by DeFronzo and colleagues (66).

Tissue Acquisition

Abnormalities in endothelium-dependent vasodilation have been demonstrated in humans in peripheral and coronary conduit arteries, peripheral and coronary resistance arterioles, and in skin microvessels of patients with diabetes (67-70). Therefore, we will biopsy easily accessible arm skin microvessels to determine the effects of each intervention on endothelial insulin signaling. The skin will be cleansed with betadine and draped to create a sterile field. Lidocaine 2% will be used to anesthetize a 1.2 cm ring in the arm around the biopsy site. A 6 mm bioptome will be used to obtain a

skin sample. The skin biopsy is marked for orientation and immediately frozen in liquid nitrogen and stored at –80 C for subsequent protein extraction for Western blot.

Tissue Analysis

The analyses of biopsy specimens will be performed in the laboratory of [name].

Western blotting: The analyses of the skin and muscle biopsy specimens will be performed under the direction of [name] (consultant). Skin biopsy specimens are immediately frozen in liquid nitrogen. Frozen tissues are homogenized using a Polytron homogenizer in lysis buffer (71). After 30 min of incubation on ice, samples are centrifuged for 20 min at 14,000 g at 4°C to yield a solubilized preparation. Protein concentration is measured by using a protein assay (Bio-Rad; Richmond, CA). Equal quantities of protein from each sample (10 µg) are resolved by SDS-PAGE on 9% gels and electroblotted onto nitrocellulose. After incubation overnight with 5% bovine albumin -Tris-buffered saline with 0.1% Tween 20 (TBST), membranes are incubated for 1 h with the specified primary antibody [(monoclonal anti-eNOS or anti-Akt antibodies at 1:10,000 dilution, Transduction Laboratories) or (polyclonal phospho-eNOS Ser1179 or phospho-Akt antibodies at 1:5,000 dilution; Cell Signaling)]. After several washes, the membranes are incubated for 1 h with a horseradish peroxidase-labeled goat anti-rabbit (for phospho-Akt or phospho-eNOS Ser1179) or anti-mouse (for total Akt or total eNOS) immunoglobulin secondary antibody (Pierce Chemical). After being washed 10–15 additional times, the membranes are incubated with a chemiluminescent reagent according to the manufacturer's protocols (SuperSignal West Femto; Pierce Chemical) and exposed to X-ray film.

Immunodetection: Serial 4 µM sections of skin biopsy sections are deparaffinized, hydrated, and serially incubated in citrate buffer, H₂O₂, blocking solution, primary antibody, and appropriate secondary antibody, with intervening washes. The ABC biotin/avidin method with Nova Red substrate is utilized for immunodetection (Vector Labs). Primary antibodies include: total Akt (Cell Signaling), phospho-specific Akt (Ser 473, Cell Signaling), total eNOS (Transduction Labs), and phospho-specific eNOS (Ser 1177, Cell Signaling). When available, blocking peptide is incubated with primary antibody in a separate section to ensure specificity of staining. If blocking peptide is not available, additional sections are incubated without primary antibody. To ensure localization of identified signal in vascular cells, additional sections will be processed for immunofluorescence and colocalization with primary antibodies directed against the endothelium-specific von Willebrand factor (Santa Cruz Biotechnology). Images will be viewed using an AX70 Olympus Microscope with Phase 3 Imaging System (Image Pro 4.0 software) or the Zeiss LSM-410 Invert Laser Scan confocal microscope with imaging software (Matrox Image-Series Utilities).

Assays for markers of inflammation, insulin, free fatty acids

Plasma samples from insulin resistant and healthy subjects will be assayed for high sensitivity CRP (hsCRP), tumor necrosis factor-α (TNF-α), and interleukin-6 (IL-6) using the respective ELISA kits (Sigma; Endogen, Woburn, MA; BenderMedSystems; Vienna, Austria). Plasma insulin concentration will be measured using an Immunoenzymatic Sandwich Assay (Beckman Coulter, Inc.). Acrylodan-labeled Intestinal Fatty Acid Binding Protein (ADIFAB), a fluorescent molecule, will be used to assay the concentration of free fatty acids. The assay is accurate to about 1nM (72). All assays will be performed in duplicate by investigators blinded to the status of the subject (metabolic syndrome or control) and treatment.

BIOSTATISTICAL ANALYSIS

Statistical Analysis

Sample size calculation: All specified protocols employ a randomized, placebo-control cross-over design. Given the paired-design, the sample sizes have been calculated using estimates of the difference in flow-mediated, endothelium-dependent vasodilation after placebo and active treatment.

Table 2: Calculated Power For a Given Effect Size and Standard Deviation
Standard Deviation

Treatment Effect	3.5%	4.0%	4.5%
2.5%	.97	.91	.84
3.0%	.99	.98	.94
3.5%	1.0	.99	.98

endothelium-dependent vasodilation (i.e., the change in brachial artery vasodilation) between active therapy and placebo, will be assessed using repeated measures ANOVA (73). All analyses will employ the intention-to-treat principle. The treatment “order effect” will be explored by examining the interaction between treatment group (e.g. acipimox vs. placebo) and sequence of treatment (placebo first vs. active therapy first).

Baseline characteristics of treatment and control patients will be compared using Student’s t-test or non-parametric tests, depending on the distribution of the data. To examine whether the active therapy has similar effects on flow-mediated vasodilation between healthy subjects and those with the metabolic syndrome, we will test the interaction between treatment group and the metabolic syndrome (yes/no). In secondary analyses, we will assess the effects of active therapy on eNOS phosphorylation, insulin sensitivity, and plasma inflammatory markers such as CRP, IL-6, and TNF- α . We will assess the relationship between the change in eNOS phosphorylation and changes in endothelium-dependent vasodilation using linear regression analyses, controlling for age, and gender. Likewise, we will examine the relationship between changes in insulin-mediated vasodilation and insulin-sensitivity associated with active treatment. Multiple analysis of variance (MANOVA) will be used to examine the main and interaction effects of categorical variables on multiple dependent variables, and multiple analysis of covariance (MANCOVA) for continuous independents. Thus, in the analyses, we can include vascular function and other outcomes simultaneously as dependent variables in the models. If the dependent variables are uncorrelated with each other, repeated measure ANOVA for each dependent variable will be employed.

Data interpretation: Vascular function will be determined after each intervention. Each intervention will be studied individually. If flow-mediated vasodilation is restored after an intervention (acipimox) compared with placebo, it will be interpreted that FFA impairs endothelial insulin signaling and decreases endothelium-dependent vasodilation. This interpretation will be confirmed by cutaneous tissue testing. If eNOS serine₁₁₇₇ phosphorylation is increased after an intervention compared to placebo, it will be interpreted that improved activation of the PI3-kinase

Based on previous studies, we expect to find an absolute difference in flow-mediated, endothelium-dependent vasodilation of the brachial artery between the test agent and placebo of 3% with an estimated standard deviation of 4% (68). With a 2-sided alpha error of 0.05 and a power of 90%, 30 subjects in each group of each protocol should find at least this difference in the primary endpoint (Table 2).

Statistical methods: All descriptive data will be expressed as means \pm standard deviation. The primary endpoint of change in flow-mediated,

pathway increases eNOS phosphorylation and resultant NO production. This interpretation will be supported if multivariate linear regression analysis defines a significant positive relationship between changes in eNOS phosphorylation and vascular and/or skeletal muscle metabolic function. If endothelium-dependent (flow-mediated) or insulin-mediated vasodilation remains similar despite an intervention (acipimox), it will be interpreted as a lack of effect of the agent on endothelial-insulin signaling and vascular function. If any intervention increases vasodilation to nitroglycerin, it will be interpreted that the intervention has improved vascular smooth muscle function. If the intervention improves vascular function in both subjects with the metabolic syndrome and healthy subjects, this will be interpreted as a generalized effect, independent of the metabolic syndrome.

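### The treatment-by-metabolic-syndrome test on flow-mediated vasodilation compares non-randomised groups without age or sex adjustment, so any age or sex difference in drug response enters the interaction estimate.

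*Combined protocol and SAP*

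**What the plan says.** Under Study Procedures and Protocol, each subject receives acipimox and placebo in random order. What is randomised is the order of treatment. Whether a subject has the metabolic syndrome is a characteristic the subject brings to the trial.

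Under Biostatistical Analysis, Statistical methods, the plan asks whether the drug acts similarly on FMD in healthy subjects and in those with the syndrome: "we will test the interaction between treatment group and the metabolic syndrome (yes/no". No covariate is attached to this test. Later in the same paragraph, the regression of FMD change on eNOS phosphorylation change is run "using linear regression analyses, controlling for age, and gender". Baseline characteristics are compared by t-test or a non-parametric test, with no stated consequence for any model. MANCOVA is offered in general terms for continuous predictors; neither age nor sex is named there, and it is not tied to the interaction.

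The sample size rests on the paired difference alone: "Given the paired-design, the sample sizes have been calculated using estimates of the difference in flow-mediated, endothelium-dependent vasodilation after placebo and active treatment". The plan gives no calculation for the interaction.

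Data interpretation states that if vascular function improves in both groups, "this will be interpreted as a generalized effect, independent of the metabolic syndrome".

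**The concern.** The interaction amounts to a two-sample comparison of drug-minus-placebo differences, healthy subjects against subjects with the syndrome. Pairing cancels anything that shifts a subject's FMD equally under both treatments. It does not cancel anything that changes how much the subject responds to the drug. If the groups differ in age or sex and response varies with either, that part of the difference is attributed to the syndrome.

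Two errors are possible. A difference that really belongs to age or sex could appear as a difference by syndrome status, or it could offset a true difference and hide it. The plan already treats age and gender as relevant to change in FMD in a neighbouring analysis, so leaving them out here looks like an oversight.

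**Working it through.** **Inputs from the documents.** The Sample size text gives an effect and SD "between the test agent and placebo of 3% with an estimated standard deviation of 4% (68", two-sided alpha 0.05, and "30 subjects in each group of each protocol". I read the last as 30 subjects with the syndrome and 30 healthy subjects.

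**Check of the plan's own figure.** A paired t-test with n = 30, difference 3 and SD of the difference 4 has noncentrality 3/(4/√30) = 4.11 on 29 df. Power is 0.978, against .98 in Table 2. All nine cells reproduce to within 0.01. The 4% is therefore the SD of the within-subject difference, which is the SD the interaction needs.

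**Interaction without confounding.**
- SE = 4 × √(2/30) = 1.03 points, assuming the same SD in both groups.
- 95% CI half-width = 2.00 × 1.03 = 2.07 points.
- Power is 81.5% for a true 3-point difference between groups (noncentral t, 58 df) and 48% for 2 points.

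**Assumptions for the bias.** The documents give no age or sex distribution by group and no dependence of response on either. I assume that the groups' mean ages differ by d = 0.5 or 1 SD and that age explains R² = 1%, 5% or 10% of within-group variance in response.

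Bias = √R² × 4 × d. Rejection is for a nominal 5% test with no true interaction. Power is for a true 3-point interaction when the bias opposes it.

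| R² | d | Bias (points) | Rejection | Power |
|---|---|---|---|---|
| 1% | 0.5 | 0.20 | 5.4% | 76% |
| 1% | 1 | 0.40 | 6.7% | 70% |
| 5% | 0.5 | 0.45 | 7.1% | 68% |
| 5% | 1 | 0.89 | 13.6% | 52% |
| 10% | 0.5 | 0.63 | 9.2% | 62% |
| 10% | 1 | 1.26 | 22.6% | 38% |

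**Sex, also assumed.** A 30-point gap in the share of one sex and a 2-point difference in response by sex give a bias of 0.3 × 2 = 0.6 points, 8.8% rejection, and 63% power for an opposing 3-point interaction.

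**Does adjustment work?** In simulation (5,000 runs per scenario, age SD 10 years, slopes of 1.0 or 1.5 points per decade), age and sex were entered as covariates for the within-subject difference. At gaps of 0 to 15 years with no true interaction, type I error was 4.7% to 5.4% and bias was near zero. With a true 3-point interaction and opposing confounding from gaps of 10 or 15 years, the adjusted model had 66% to 77% power.

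**Precision cost.** For age alone, variance inflation is 1 + d²/4: 1.06 at d = 0.5 and 1.25 at d = 1, so the SE is multiplied by 1.03 or 1.12. Now add a 35% v 65% sex split, uncorrelated with age. Its squared standardised gap is 0.3²/(0.35 × 0.65) = 0.40. The inflation becomes 1 + (0.25 + 0.40)/4 = 1.16 or 1 + (1 + 0.40)/4 = 1.35, and the SE is multiplied by 1.08 or 1.16.

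**The case against.** A reader might infer that the plan derives its conclusion of independence from the syndrome from this interaction test, so that confounding undermines that conclusion directly. The text does not support that. Data interpretation triggers the phrase when function improves in both groups. Each of those improvements is an acipimox-placebo contrast within subjects, protected by the randomised crossover, and an age or sex gap between groups cannot manufacture both. The plan states no conclusion that follows from a significant interaction. This objection stands, and the point is confined to the interaction estimate.

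A reader might also infer that the groups are unmatched. The supplied text describes no matching, but it has no eligibility or recruitment section, which is where matching would appear. Its absence from the plan as a whole cannot be established.

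The size is entirely assumed. Bias needs both a group gap and a response that depends on the same variable. If age explains only 1% of response variance, rejection is 5.4% to 6.7%, close to nominal.

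Finally, the MANCOVA sentence could accommodate age. It does not commit to age or sex, however, and a main-effect term in the repeated-measures model would not help: the confounding acts on the response to treatment, so the term has to interact with treatment.

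**Conclusion.** The concern holds as a gap in one non-primary analysis. The interaction compares groups that were not randomised, its specification names neither age nor sex, and the plan adjusts for both nearby. Under the assumed age gaps and R² values, bias is 0.2 to 1.3 points against an expected treatment effect of 3 points, the 5% test rejects about 5% to 23% of the time, and power for a true 3-point interaction falls from 81.5% to between 76% and 38% when the bias opposes it. The direction is unknown. If the groups are balanced on age and sex, or response does not vary with either, the bias is zero.

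The documents do not show that the bias exists, and they do not put the primary within-subject comparison in doubt. This is a worthwhile, low-cost improvement and not a flaw that threatens the trial's main result.

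**What to change.** Keep the planned interaction test. Prespecify a second model that adds treatment-by-age and treatment-by-sex terms or, equivalently, enters age and sex as covariates for the within-subject difference. Report both interaction estimates with 95% CIs. If the groups are matched on age and sex, say so in the analysis section.

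Describe the result as a difference, or no detected difference, between the groups studied. Attribute it to the syndrome only with the caveat that confounding by other factors remains. Agreement between the two models should not be used to license a claim of independence from the syndrome. Both could agree on a large group difference, or both could lie near zero with intervals of about ±2 points.

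The cost is one extra model on age and sex, which the plan already uses, and two degrees of freedom. The SE in the adjusted model is about 3% to 16% larger, depending on the age and sex gaps assumed above; an age gap wider than 1 SD would cost more.

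### The secondary change-on-change regressions leave out treatment sequence, so period effects present in both outcomes would bias the slope that is read as support for the mechanism

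*Combined protocol and SAP*

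**What the plan says.** Study Procedures and Protocol sets out a two-period crossover: "Subjects will be studied at 2 separate visits, 4 weeks apart, in a randomized, double-blind crossover design". Both outcomes of the main regression are collected on both occasions: "Each visit will include vascular function testing and a forearm skin biopsy".

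Under Statistical methods, the plan relates the change in eNOS phosphorylation to "changes in endothelium-dependent vasodilation using linear regression analyses, controlling for age, and gender". The next sentence says that the investigators will similarly "examine the relationship between changes in insulin-mediated vasodilation and insulin-sensitivity associated with active treatment". It lists no covariates of its own; at most it carries over age and gender.

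The Data interpretation section gives the first regression a stated use. The proposed pathway counts as supported if "multivariate linear regression analysis defines a significant positive relationship between changes in eNOS phosphorylation" and vascular or skeletal-muscle metabolic function.

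Order is considered elsewhere in Statistical methods. The plan explores the interaction of treatment with sequence for the primary endpoint, but does not carry sequence into either regression. MANOVA "will be used to examine the main and interaction effects of categorical variables on multiple dependent variables", but the text neither names sequence as one of those variables nor ties that model to the regressions.

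**The concern.** Each change is active minus placebo within a subject. For subjects who take active treatment second, the change contains the visit-2-minus-visit-1 drift; for those who take it first, it contains the negative of that drift. Sequence therefore shifts the eNOS change and the FMD change together. If both outcomes drift, subjects in one sequence tend to have both changes raised, or one raised and one lowered, and the scatter plot shows a slope that has nothing to do with biology. Age and gender cannot absorb this, because sequence is randomised independently of them.

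At stake is the corroborating step. A same-direction drift could produce a significant positive slope, read as support for the mechanism, where no link exists. An opposite drift could hide a link that does exist. The same reasoning applies to the insulin regression.

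**Working it through.** **Fixing the scale from the plan's own figures.** Inputs: expected FMD difference 3%, SD 4%, two-sided alpha 0.05 and 30 subjects per group (Sample size calculation). Read as a paired t-test, the noncentrality is 3 / (4/√30) = 4.11 on 29 degrees of freedom, giving power 0.978 against .98 in Table 2. For a 2.5% effect the result is 0.911 against .91. A two-sample reading gives 0.83 for 3%/4% and does not match. So 4% is the SD of the within-subject difference, and a shift of 0.25 or 0.5 SD is 1 or 2 FMD points (0.25 × 4; 0.5 × 4).

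**Algebra.** Code sequence s = +1 or −1, balanced. Let the eNOS change have within-sequence SD 1 and period shift pE·s, and let the FMD change have within-sequence SD 1 and period shift pF·s. With no link within sequence:

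- Covariance of the two changes = pE × pF.
- Unadjusted slope = pE × pF / (1 + pE²).
- 0.25/0.25: 0.0625 / 1.0625 = 0.059.
- eNOS 0.5, FMD 0.25: 0.125 / 1.25 = 0.10.
- 0.5/0.5: 0.25 / 1.25 = 0.20.
- 0.5/−0.5: −0.20.
- Either shift zero: 0.

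If there is a true slope b, the bias has the same form, with pF replaced by the part of the FMD shift not transmitted through eNOS. For example, with b = 0.3, an eNOS shift of 0.5 and a direct FMD shift of −0.5, the expected unadjusted slope is 0.3 − 0.25/1.25 = 0.10. Most of the true link is masked.

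**Simulation.** FMD change is regressed on eNOS change with age and gender, balanced sequences and no true link. The table gives the chance of a significant positive slope (nominal 2.5%). Thirty subjects is one group; 60 is both groups pooled. The shift sizes are assumptions.

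| Shifts (SD of each change) | 30 subjects | 60 subjects |
|---|---|---|
| 0.25 and 0.25 | about 5% | about 6% |
| 0.5 and 0.25 | 8% | 13% |
| 0.5 and 0.5 | 18% | 33% |
| 0.5 in one outcome only | about 2.5% | about 2.5% |
| 0.25 and −0.25 | about 1% | about 1% |
| 0.5 and −0.5 | about 0.1% or below | about 0.1% or below |

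With sequence added as a covariate, the rate returns to about 2-3% and the mean slope to about zero in every row.

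**The case against.** The strongest reply is that nothing in the documents suggests a period effect of damaging size. A 0.5 SD shift is 2 FMD points between visits, two-thirds of the 3% drug effect the trial is designed to find. The reported reader variability (0.05 ± 0.16% between and 0.01 ± 0.15% within observers) makes image reading an unlikely source. Specimens are frozen for later processing. The bias also needs drift in both outcomes, in the same direction, before it yields a false positive. All of this stands as a limit on size. It does not rule out biological or procedural drift, and sequence is specified in advance because drift cannot be known beforehand.

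A second reply is that age and gender may not be a closed list, and that order is already explored. But they are the only covariates named, and the exploration concerns the treatment comparison, not the regressions.

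Three stronger readings are tempting, and the documents do not support them.

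- A reader might take 33% as the expected false-positive rate. It is the unfavourable corner of an assumed range, needing equal, same-direction shifts of 0.5 SD and pooled groups.
- A reader might infer that the primary analysis is flawed, because the difference "between active therapy and placebo, will be assessed using repeated measures ANOVA" with no statement that period is kept. In this design the treatment-by-sequence contrast that the plan explores is the period contrast. With 15/15 sequences, leaving period out causes no bias, and type I error is conservative (about 3% at a 2-point shift). Power for a 3% effect is still 0.96.
- A reader might infer confounding by metabolic-syndrome status. That arises only if the groups are pooled and both changes differ between groups. Sizing is per group ("30 subjects in each group of each protocol should find at least this difference in the primary endpoint"), and pooling is not stated. Whether to adjust for group is then a choice of estimand.

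**Conclusion.** The point holds as a minor one. Neither regression names sequence, and both changes in each come from the same ordered visits. With no true link, the covariance between the changes equals the product of the two period shifts. The resulting false-positive rate runs from about 0.1% or below, through the nominal 2.5% when only one outcome shifts, to 18% (30 subjects) or 33% (60) in the unfavourable case. At 0.25 SD in both outcomes the excess is small. These rates rest on assumed shifts, balanced sequences and normal errors; the documents give no period effect and no SD for the eNOS change.

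Only the corroborating slope is exposed. The randomised effects on FMD and on eNOS phosphorylation carry the main conclusion and do not depend on it.

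**What to change.** Add treatment sequence as a covariate, alongside age and gender, to both change-on-change regressions: eNOS phosphorylation with FMD, and insulin-mediated vasodilation with insulin sensitivity. This is a change of SAP wording; it needs no new data and does not alter the sample size.

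The cost if there is no period effect is about 0.01-0.02 in power to detect a true slope:

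- 60 subjects: 0.64 to 0.63 at a correlation of 0.3, and 0.89 to 0.88 at 0.4.
- 30 subjects: 0.34 to 0.33 at 0.3, and 0.58 to 0.56 at 0.4.

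Two wording notes can be settled in the same edit, though the point does not rest on them: say whether the period term stays in the primary FMD model, and whether the regressions pool the two groups.
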